### 8.3 Sample Size

Because the efficacy of eltrombopag in this subject population is unknown, we would like to reject the treatment as quickly as possible with a small number of subjects if the treatment is not effective. In our past experience with this patient population, a novel treatment with a response rate 30% or more would generally warrant further investigation, while the treatment would be rendered non-effective if it has a response rate of 10% or less. We will use Simon's Two-Stage Minimax Design with a response probability of 10% or less to terminate the treatment and the hypothesized actual response probability of 30% or more. The sample size is determined by testing the null hypothesis  $H_0: p \leq 10\%$  versus the alternative  $H_1: p \geq 30\%$  at a significance level of 0.05 and a power of 0.8. At the first stage, 15 subjects will be accrued. Further accrual will be halted until the all 15 subject reach the 16 to 20 weeks response time point. The null hypothesis will not be rejected if no more than 1 subject responds to the treatment within 16 to 20 weeks. If 2 or more subjects respond to the treatment within 16 to 20 weeks at the first stage, then an additional 10 subjects will be accrued, bringing the total number of subjects to  $n = 25$ . The null hypothesis of  $p \leq 10\%$  will be accepted if the total number of responders within 4 months is 5 or less.

**Subjects who discontinue the study drug prematurely (before 20 weeks):** Platelet count measurement will be attempted even if a subject discontinues study drug. Important covariates for this study include age, karyotype, IPSS score, duration of platelet transfusion dependence, marrow cellularity and TPO level. The Cox proportional hazard model will be applied to time-to-event variables, such as time-to-death, time-to-relapse and time-to-progression. Since the sample size is relatively small, we will mostly consider Cox models with a single continuous or categorical covariate to ensure reasonable statistical accuracy. Such analysis is exploratory in nature and aimed at generating statistical hypothesis for future studies. Subjects who withdraw from the study for reasons other than lack of efficacy or toxicity (rendering platelet count missing) may be replaced. All other subjects should be evaluable for efficacy (i.e. all subjects who withdraw for treatment related concerns prior to end of week 16 or 20 assessment for toxicity or failure to respond will be counted as non-responders at the primary time points (intent to treat paradigm)). Based on the assumed dropout rate of 15-20% and the goal of having 25 evaluable subjects, 5 additional subjects may be enrolled.

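### Section 8.3 lets some withdrawn subjects leave the efficacy denominator under an intent-to-treat label and still tracks only platelets, so the reported response rate can be inflated

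*Combined protocol and SAP*

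**What the plan says.** The early-discontinuation paragraph of section 8.3 sorts subjects by why they left.

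- **May be replaced:** "Subjects who withdraw from the study for reasons other than lack of efficacy or toxicity (rendering platelet count missing) may be replaced". Everyone else is described as evaluable for efficacy, which implies that replaced subjects are not.
- **Kept as failures:** those leaving over toxicity or failure to respond "will be counted as non-responders at the primary time points (intent to treat paradigm".
- **Measured after stopping drug:** "Platelet count measurement will be attempted even if a subject discontinues study drug". No other count and no transfusion record is named.

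The same paragraph assumes 15-20% dropout and allows 5 subjects beyond the 25 evaluable. Section 8.4 sets a protocol ceiling of 30 and keeps the first 5 patients out of the primary analysis, because Amendment L changed eligibility and moved erythroid and neutrophil responses into the primary criteria. Section 8.2 defines response in all three lineages.

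Section 6.4 schedules a CBC with differential at weeks 1, 2 and 3 and at 1 and 6 months after the last dose, for subjects off drug for a section 8.6 reason.

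**The concern.** An analysis set chosen by reason for leaving is not intent to treat. Section 8.3 does not say who classifies the reason. Section 9.2.3 provides an independent monitor for attribution of treatment-related serious events, but not for withdrawals. Replacement is also optional, so it can be decided case by case in an open-label, single-arm trial.

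Section 8.6 lists reasons that are neither toxicity nor lack of efficacy by name but may go with a poor outcome: starting other MDS therapy, a concomitant condition, non-compliance and loss to follow-up. Section 8.3 does not say how these count.

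The platelet wording leaves a second gap. A subject enrolled for anemia or neutropenia has no clear rule for when the outcome is missing or what is collected after stopping.

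At stake is whether the published rate describes everyone treated or a selected subset. With about 25 subjects, a few removals move it by several percentage points.

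**Working it through.** **Inputs.** Section 8.3 specifies Simon's minimax design "with a response probability of 10% or less to terminate the treatment and the hypothesized actual response probability of 30% or more", "at a significance level of 0.05 and a power of 0.8". "At the first stage, 15 subjects will be accrued"; "The null hypothesis will not be rejected if no more than 1 subject responds to the treatment within 16 to 20 weeks"; otherwise "an additional 10 subjects will be accrued, bringing the total number of subjects to" 25. Success needs 6 or more responders. Dropout is 15-20% (section 8.3), not split by reason. The ceiling is 30, with 5 excluded (section 8.4).

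**1. Reproduce the design.** The chance of success at response rate p is

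R(p) = Σ (x = 2 to 15) P(Bin(15, p) = x) × P(Bin(10, p) ≥ 6 − x).

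R(0.10) = 0.0328 and R(0.30) = 0.8017. A full search returns the same minimax design (1/15, 5/25). The plan's figures stand.

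**2. Count the places.**
- Enrolment needed for 25 evaluable: 25/0.85 = 29.4, so 30; 25/0.80 = 31.25, so 32. The allowance of 25 + 5 = 30 fits 15% dropout and is 2 short at 20%.
- Places open to the primary analysis: 30 − 5 = 25. None remain for replacements.
- Evaluable out of 25: 25 × 0.85 = 21.25; 25 × 0.80 = 20.

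**3. Effect within 25 places.** Suppose all dropouts are non-responders and are removed. The minimum success of 6/25 = 24.0% becomes 6/21 = 28.6% or 6/20 = 30.0%. The upper figure equals the plan's target rate.

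Removing a non-responder adds no responder, so the 6-responder threshold is no easier to reach. With the first look at 15 treated subjects, type I error against a 10% all-treated rate stays at 3.28%. If that look waited for 15 evaluable subjects, success would still require at least 6 responders among 25 treated, so the error could not exceed P(Bin(25, 0.10) ≥ 6) = 3.34%.

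**4. Effect if replacement went beyond the ceiling.** If a share d of enrolled subjects is replaced and none would have responded, an all-treated rate of 10% appears as 0.10/(1 − d).

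| d | apparent rate | chance of success |
|---|---|---|
| 0 | 10.0% | 3.3% |
| 5% | 10.5% | 4.1% |
| 10% | 11.1% | 5.1% |
| 15% | 11.8% | 6.4% |
| 20% | 12.5% | 8.2% |

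**5. Power with 25 places.** If every dropout counts as a failure and completers respond at 30%, the all-treated rate is 0.30 × 0.85 = 0.255 or 0.30 × 0.80 = 0.24. R(0.255) = 0.638 and R(0.24) = 0.571, against the stated 0.80.

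**6. What follow-up supplies.** Section 6.4 gives hemoglobin and ANC, but timed from the last dose. The 1-month visit with its 1-week window reaches about week 5 after stopping, so a subject who stops before about week 11 (16 − 5) has no scheduled CBC at week 16. The next visit is at 6 months. Section 6.4 lists no transfusion record, although the erythroid criterion can turn on PRBC units over 8 weeks and the platelet criterion on transfusion independence.

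**The case against.** The strongest reply has four parts.

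- **Inflation is conditional.** This is correct. Replacement is optional, withdrawals for toxicity or failure to respond are kept as failures, and if replaceable withdrawal is unrelated to response the evaluable rate is unbiased and type I error stays at 3.3%. A reader might infer that the rate is inflated; the documents support only that it can be.
- **The ceiling limits the damage.** This is also correct. A reader might take the 5 extra subjects at face value and infer 5 of 30 treated replaced, an apparent rate of 0.10 × 30/25 = 12% and a type I error of 7.0%. Section 8.4 leaves 25 places, so that trial cannot be run as written.
- **Blood counts are collected after discontinuation.** This is correct for hemoglobin and ANC. A reader might infer from section 8.3 that erythroid and neutrophil outcomes are lost by design, but section 6.4 contradicts that. The timing and transfusion gaps remain.
- **The set of replaceable subjects may be narrow.** Section 8.6.1 speaks of withdrawal by subject choice, while non-compliance and non-protocol therapy fall under investigator decision in 8.6.2, so they need not be replaceable. This shows that the text is ambiguous, not that it is safe.

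A further objection is that counting all withdrawals as failures costs power. With 25 places and a fixed threshold of 6, dropping a non-responder and counting one as a failure lead to the same final decision. The shortfall comes from the ceiling, not from the choice of denominator.

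**Conclusion.** The concern holds in a limited form. Section 8.3 permits a denominator that depends on the reason for withdrawal, mislabels it, and was not brought into line with the three-lineage endpoint.

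Under the current ceiling the exposure is in the reported rate: 24% of those treated could appear as 29-30%. This assumes that the whole 15-20% dropout is replaceable and that none would have responded, so it is an upper range. The go/no-go decision is essentially unaffected. Type I error would pass 5% only if replacements were allowed beyond the ceiling and about 10% of enrolled subjects were replaced non-responders.

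The conflict between the 5 additional subjects and the 25 remaining places stands whatever the reasons for withdrawal. At the assumed dropout only about 20-21 subjects would be evaluable, short of the goal of 25.

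**What to change.** 1. Define the primary analysis set as all treated post-Amendment-L subjects and count any missing week 16/20 response as non-response. Show the evaluable-set result as secondary.
2. In both sentences of section 8.3 that name the platelet count, name platelet count, hemoglobin, ANC and transfusion record instead.
3. Reconcile the 5 additional subjects with the ceiling of 30. If the ceiling stays, state that with 25 places and 15-20% dropout, power against a 30% rate among completers is about 64-57%, not 80%.

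The cost is revised wording, one further table, a slightly less favourable reported response rate and a lower stated power. Restoring the power would mean revisiting the ceiling and the sample size.

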### 8.4 Statistical Methods

The time to responses will be analyzed using appropriate tools in survival analysis, such as cumulative incidence estimate and Cox regression type analysis for covariates. Important covariates for this study include age, karyotype, IPSS score, duration of platelet transfusion dependence, marrow cellularity and TPO level. The Cox proportional hazard model will be applied to time-to-event variables, such as time-to-death, time-to-relapse and time-to-progression. Since the sample size is relatively small, we will mostly consider Cox models with a single continuous or categorical covariate to ensure reasonable statistical accuracy. Such analysis is exploratory in nature and aimed at generating statistical hypothesis for future studies. Graphical tools will be used to display the appropriate estimates (i.e. estimated proportions, the cumulative incidence curves, Kaplan-Meier curves) and their corresponding 95% confidence intervals. Methods based on univariate and/or multivariable regression, analysis of variance, and logistic regression with the above covariates will also be employed if deemed appropriate. For example, a logistic regression model will be used to evaluate which patients will have a higher probability of response at 16 to 20 weeks or at an extended time period. Again, since the sample size is small, it is likely that categorical covariates

specified by certain threshold values will be employed, and exploratory data analysis techniques, such as classification and regression trees, will be used to evaluate the threshold choices.

The 5 patients accrued to date will not be included in the primary analysis of the Two-Stage Minimax Design, but will be included as an exploratory analysis for the endpoints considered. Amendment L submitted on 2/13/2013, included revisions to the eligibility criteria to include MDS patients with anemia and revisions to the primary response criteria to also include erythroid and neutrophil responses (which prior to Amendment L were secondary response criteria). Given the significant changes to the protocol it was decided it would not be appropriate to include the first 5 patients in the primary analysis. The accrual ceiling for the protocol is 30 subjects, so this will allow for the goal of having 25 evaluable subjects. The review of Amendment of L included both a Scientific and Statistical review, both of which were approved, and the IRB approved Amendment L on 5/13/2013.

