Because, severe dysfunction of megakaryocytes is the cause of thrombocytopenia in MDS patients, and because of the efficacy demonstrated in ongoing ITP clinical trials and subsequent FDA approval for use in ITP, we now propose this Phase 2, non-randomized pilot study of eltrombopag in patients with MDS. We hypothesize that the drug will stimulate more robust platelet production from the dysplastic megakaryocyte pool, and also potentially help drive primitive hematopoietic stem and progenitor cells to produce more megakaryocytes. In addition, this agent is likely to produce trilineage responses as it acts at the level of the hematopoietic stem cell. Ancillary studies will address questions such as identification of clinical and laboratory predictors of response, as well as cellular and molecular mechanism of eltrombopag action and the mechanism by which

[figure not shown]
megakaryocyte function is impaired in MDS.

We therefore propose this non-randomized, pilot, phase II study of eltrombopag in low to Int-2 risk MDS patients with cytopenias that persists despite treatment with standard therapies to assess its effectiveness in this population.

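### Section 8.4 leaves tree-chosen covariate cuts to be judged on the subjects that chose them, with no allowance for the search, so unrelated continuous covariates will often look predictive of response

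*Combined protocol and SAP*

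**What the plan says.** Section 8.4 (Statistical Methods) lists six covariates: "Important covariates for this study include age, karyotype, IPSS score, duration of platelet transfusion dependence, marrow cellularity and TPO level". It then says that "logistic regression with the above covariates will also be employed if deemed appropriate", and gives the example that "a logistic regression model will be used to evaluate which patients will have a higher probability of response at 16 to 20 weeks", or over a longer period.

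On how the covariates enter, it says: "Again, since the sample size is small, it is likely that categorical covariates" defined by threshold values will be used. Exploratory techniques, "such as classification and regression trees, will be used to evaluate the threshold choices".

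The section names no hold-out set, cross-validation, minimum node size, pre-set cut or selection-adjusted test. It gives no significance level, no form of test and no rule for declaring a covariate predictive. Earlier in the same section the covariate work is called exploratory and hypothesis-generating. Section 8.3 sets 25 subjects for the primary analysis. Section 8.4 adds the first five patients to the exploratory analyses, so the predictor analysis could have 30.

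**The concern.** A classification tree picks the cut that best separates responders from non-responders in the data it is given. If the resulting two-level covariate then goes into a logistic model on the same subjects, the ordinary p-value and interval treat the cut as if it had been fixed before the data were seen. In fact it is the best of 12 to 24 candidate cuts. The test is too liberal and the odds ratio is biased away from 1, even when the covariate has nothing to do with response.

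The small sample is given as the reason for categorising, but it points the other way. Splitting a continuous covariate discards information, and a small sample can least afford that.

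At stake is the stated purpose of the analysis. Cut-points and odds ratios produced this way would be carried into later studies as hypotheses, with their strength overstated.

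**Working it through.** **Inputs from the documents.** n = 25 (15 + 10), and response rates of 10% and 30% (section 8.3). n = 30 is possible with the first five patients (section 8.4). Four of the six covariates are continuous or nearly so: age, duration of platelet transfusion dependence, marrow cellularity and TPO level. Karyotype and IPSS fall into a few groups (Appendix B).

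**Assumptions, because the plan is silent.** Two-sided 5% level; Gini splitting, one split; cut chosen and tested on the same subjects; a covariate without ties, independent of response.

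**The plan's own figure.** Section 8.3 gives no error rate for predictors, only for the two-stage test. With X ~ Bin(15, p) and Y ~ Bin(10, p), the chance of rejecting is the sum over x = 2 to 15 of P(X = x) × P(Y ≥ 6 − x). This is 0.0328 at p = 0.10 and 0.8017 at p = 0.30. An exhaustive search finds no smaller n that meets 0.05 and 0.80. The stated design is reproduced, and nothing below alters it.

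**Step 1: choosing the cut.** Order subjects by the covariate. For a cut after subject k, let m = n − k, let a and c be the responders below and above the cut, and let R = a + c. With g(x, N) = 2(x/N)(1 − x/N), the tree takes the k that maximises g(R, n) − [(k/n) g(a, k) + (m/n) g(c, m)].

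**Step 2: testing it as if fixed.** Apply the likelihood-ratio, score, Fisher or Wald test to the resulting 2×2 table and count p < 0.05. There were 6,000 simulated trials per setting; the largest Monte Carlo standard error is about √(0.47 × 0.53 / 6000) = 0.006.

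False-positive rates (%), n = 25:

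| Cuts allowed | 30% response: LR / score / Fisher / Wald | 10% response: LR / score / Fisher / Wald |
|---|---|---|
| All 24 | 46.6 / 39.3 / 18.6 / 12.7 | 38.3 / 40.8 / 9.0 / 4.5 |
| Middle 80% | 45.8 / 36.7 / 17.1 / 11.8 | 28.8 / 33.6 / 8.3 / 4.5 |
| Middle 60% | 35.7 / 27.6 / 15.1 / 12.8 | 20.4 / 26.2 / 6.3 / 2.0 |
| At least 7 per side (12 cuts) | 26.6 / 21.2 / 11.4 / 10.8 | 20.2 / 14.0 / 3.3 / 1.9 |
| Four-level covariate (3 cuts) | 18.7 / 12.3 / 5.6 / 5.1 | 11.4 / 6.8 / 1.7 / 1.3 |
| Median, fixed beforehand | 7.2 / 5.6 / 3.8 / 2.6 | 7.0 / 1.8 / 0.9 / 0.0 |

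The last row is the comparator. Its small likelihood-ratio excess is a small-sample effect, not selection. With n = 30, 30% response and all cuts, the rates are 48 / 40 / 21 / 15.

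**Step 3: the estimate, with no test or level needed.** Same null setting, n = 25, 30% response, 0.5 added to each cell, 20,000 trials. The odds ratio is taken in whichever direction it fell. Its median is about 3.5 to 7 with a tree-chosen cut (minimum node 7 down to 1) and about 1.7 with a fixed median split. The median apparent difference in response rate at the chosen cut is 27 to 43 percentage points.

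**Step 4: does the remedy work?** A permutation test that repeats the cut search has attained size 3.4-4.9% with 3, 6, 8 or 11 responders among 25.

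**Step 5: cost of categorising.** The effects here are assumed. At 30% response at the covariate mean, power is 44% with a continuous covariate against 31% with a fixed median split (odds ratio 2.2 per SD), and 69% against 50% (odds ratio 3.3 per SD).

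**The case against.** The best defence is that the plan claims little for this analysis. The covariate work is labelled exploratory, the trees are called exploratory techniques, categorisation is only likely, and the regressions depend on being judged appropriate. Evaluating thresholds could mean checking candidate values rather than searching for them. The 95% intervals mentioned in section 8.4 belong to graphs of proportions and time-to-event curves; no p-values or intervals for tree-cut covariates are promised. Single continuous covariates are already allowed in the Cox models. No primary decision or stopping rule uses the output.

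Most of this stands, and it limits the severity. It does not remove the bias: the label warns the reader but leaves the estimate uncorrected, and Step 3 needs no p-value. With no other data set and no candidate cuts named, searching the trial's own data remains the natural reading.

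Three stronger readings are tempting but not supported:

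- **One false-positive rate for the plan.** Section 8.4 fixes neither test nor level. The rate runs from about 2% (Wald, 10% response) to 47% (likelihood ratio, 30% response).
- **At least one false predictor is more likely than not.** For four independent noise covariates at 30% response, 1 − (1 − q)^4 is 72-92% with likelihood-ratio q = 0.27 to 0.47, but only 37-43% with Wald q = 0.11 to 0.13. Duration of platelet transfusion dependence may also have many ties, since section 4.1 admits subjects on hemoglobin or ANC alone.
- **Most hypotheses generated would be false.** That needs an assumed share of real predictors, and the documents give none.

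The phrase in section 2.10, "identification of clinical and laboratory predictors of response", describes ancillary studies and adds no weight here.

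**Conclusion.** The concern holds as a minor-to-moderate point. Followed as naturally read, section 8.4 lets an unrelated continuous covariate look predictive far too often under a likelihood-ratio test, and two to four times too often under Fisher or Wald at 30% response. At 10% response Wald stays below 5%, and Fisher ranges from below 5% to about 9%. The overstated odds ratio is the sturdier part of the finding, because it depends on no test or level.

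The sizes rest on the assumptions listed above: one Gini-chosen split, the same subjects for choosing and testing, a 5% level, and a covariate with few ties. Karyotype and IPSS, with few levels, are much less affected. A reader might infer that the trial's efficacy conclusion is at risk. It is not: the two-stage test uses none of these covariates.

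**What to change.** In section 8.4, replace the sentence on threshold-based covariates with wording to this effect:

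- Age, duration of platelet transfusion dependence, marrow cellularity and TPO level enter the logistic models one at a time as continuous covariates.
- Categories are used only where the cut is fixed beforehand, for example the IPSS and karyotype groups in Appendix B.
- If a tree suggests a cut, it is reported descriptively without an ordinary p-value or confidence interval, or with a permutation p-value that repeats the whole cut search in each permutation.

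The cost is one paragraph and a little programming, with no new data. The continuous model assumes a roughly linear effect on the logit scale, and fewer covariates will look predictive. Penalised estimation or a log scale for TPO would be reasonable refinements, but they are preferences and not part of this point.

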Subjects must have weekly blood tests at the NIH or drawn by their referring health care provider. If subjects are to be followed at home for interim visits, progress notes and laboratory results from their health care provider and laboratory must be faxed to the study research nurse, at [name]. The following assessments will be done:

- Clinical assessment (weeks 4, 8, 12, 16, and 20\* +/- 4 days, if seen at the NIH CC only)
- Concurrent medication review (with each clinical assessment)
- CBC with differential (weekly +/- 4 days)
- Acute care, mineral and hepatic panels, CK, LDH, total protein and uric acid (weekly +/- 4 days) (Home MDs: electrolytes, transaminases, urea nitrogen (BUN), serum creatinine clearance, total bilirubin)
- Reticulocyte count (weekly +/- 4 days) (If seen at home, only if available)
- DAT (direct antiglobulin test) (as clinically indicated)
- Type and screen (as clinically indicated)
- Pregnancy test (urine or blood HCG) in woman of childbearing potential (4, 8, 12, 16, and 20\* weeks +/- 4 days)
- Bone marrow aspirate and biopsy with reticulin and collagen fiber staining and cytogenetic analysis at primary end point (morphology, cellularity, percentage of blast cells, and/or chromosomal analysis by PCR) (week 16 +/- 4 days or if clinical indicated)
- Flow cytometry of bone marrow aspirate (week 16 and 20\* +/- 4 days) (at clinician discretion)
- Flow cytometry of the peripheral blood for GPI-cells
- Lymphocyte phenotyping (TBNK flow cytometry 16 and 20\* weeks +/- 4 days)

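### The 5 places reserved for dropout in section 8.3 are used in section 8.4 for the excluded pre-Amendment L subjects, so the stated power of 0.8 holds only if no later subject is non-evaluable

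*Combined protocol and SAP*

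**What the plan says.** Section 8.3 describes a Simon two-stage minimax design testing a response rate of 10% or less against 30% or more, "at a significance level of 0.05 and a power of 0.8". Fifteen subjects enter stage 1, and the trial stops if at most 1 responds. Otherwise 10 more are enrolled, for a total of 25, and the null is retained if at most 5 respond in all.

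The same section sets the dropout allowance: "Based on the assumed dropout rate of 15-20% and the goal of having 25 evaluable subjects, 5 additional subjects may be enrolled". It also says who is lost and who is not. "Subjects who withdraw from the study for reasons other than lack of efficacy or toxicity (rendering platelet count missing) may be replaced". Withdrawals for toxicity or failure to respond, by contrast, stay in the analysis and count as non-responders: "All other subjects should be evaluable for efficacy".

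Section 8.4 then deals with the subjects enrolled before Amendment L: "The 5 patients accrued to date will not be included in the primary analysis of the Two-Stage Minimax Design". It goes on: "The accrual ceiling for the protocol is 30 subjects, so this will allow for the goal of having 25 evaluable subjects". No other part of the document gives a separate ceiling for post-amendment subjects.

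**The concern.** The two sections give the same 5 places different jobs. In section 8.3 they cover dropout (25 + 5 = 30). In section 8.4 they absorb the excluded subjects (30 - 5 = 25). Once the excluded subjects are taken out, 25 enrolled gives 25 evaluable only if nobody is lost, and the replacement rule has no place to draw on.

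Two things are at stake. First, a reader of sections 8.3 and 8.4 would take the power of 0.8 to be protected against 15-20% dropout, and it is not. The error runs towards missing an active drug. Second, the final cut-off is stated only for a total of 25. In an open-label single-arm trial, a cut-off for a smaller number could be settled when responses are already known.

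**Working it through.** **Inputs.** From section 8.3: p0 = 0.10, p1 = 0.30, n1 = 15, stop if at most 1 responder, n = 25, reject the null at 6 or more, dropout 15-20%, 5 extra places. From section 8.4: ceiling 30, 5 subjects excluded.

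**Places.** Post-amendment places = 30 - 5 = 25. Places left for dropout = 25 - 25 = 0.

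**Reproducing the stated design.** The probability of rejecting the null is the sum, over stage 1 responders x = 2 to 15, of P(X1 = x) × P(X2 ≥ 6 - x), with X1 ~ Bin(15, p) and X2 ~ Bin(n - 15, p). At p = 0.30 and n = 25:

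- x = 2: 0.0916 × 0.3504 = 0.0321
- x = 3: 0.1700 × 0.6172 = 0.1049
- x = 4: 0.2186 × 0.8507 = 0.1860
- x = 5: 0.2061 × 0.9718 = 0.2003
- x ≥ 6: 0.2784

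The sum is 0.8017. The same formula at p = 0.10 gives 0.0328. The stated alpha and power are therefore met, power by 0.2 percentage points. A search over all two-stage designs found none with 24 or fewer subjects that meets both alpha 0.05 and power 0.80.

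**Fewer than 25 evaluable.** Stage 1 is kept at 15 evaluable:

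| Evaluable | Alpha, 6 or more | Power, 6 or more | Alpha, 5 or more | Power, 5 or more |
|---|---|---|---|---|
| 25 | 3.3% | 80.2% | – | – |
| 24 | 2.7% | 76.8% | 8.2% | 88.0% |
| 23 | 2.2% | 72.9% | 7.1% | 85.8% |
| 22 | 1.8% | 68.6% | 6.1% | 83.2% |
| 21 | 1.4% | 63.7% | 5.2% | 79.9% |
| 20 | 1.1% | 58.4% | 4.3% | 76.2% |

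If the one lost subject is in stage 1 and is not replaced there (14 then 10), power is 76.5% rather than 76.8%.

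**How likely a loss is.** The plan does not split its 15-20% into evaluable and non-evaluable dropouts, so the non-evaluable rate d is an assumption and is shown as a range. The chance that all 25 are evaluable is (1 - d)^25. Averaged power weights the 6-or-more power by the binomial distribution of the number evaluable, with stage 1 refilled to 15. The comparison has 30 post-amendment places, with the analysis capped at 25 evaluable.

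| Assumed d | P(all 25 evaluable) | Averaged power, 25 places | Averaged power, 30 places | Cost in points |
|---|---|---|---|---|
| 2% | 60% | 78.4% | 80.2% | 1.7 |
| 5% | 28% | 75.6% | 80.2% | 4.6 |
| 10% | 7% | 70.3% | 79.8% | 9.5 |
| 15% | 1.7% | 64.2% | 78.1% | 13.8 |
| 20% | 0.4% | 57.6% | 74.5% | 16.9 |

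Costs are taken from unrounded powers.

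**The case against.** The strongest reply is that few subjects will be non-evaluable. Withdrawals for toxicity or lack of response stay in as non-responders. After discontinuation, "Platelet count measurement will be attempted even if a subject discontinues study drug". Section 6.2 also makes data easy to obtain: "Subjects must have weekly blood tests at the NIH or drawn by their referring health care provider". The true loss may therefore be well below 15-20%, and at 2% the cost is under 2 points. This stands, and it is why the size is given as a range. It does not remove the point: one lost subject already takes power to 76.8%, and the plan itself judged that 5 places were needed.

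A second reply is that the cut-off is written as a count of responders, so its plain reading with 24 evaluable is still 6, and nothing in the plan permits 5. That is fair. The alpha figures for 5 or more show what a departure would do, not what the plan prescribes. One confirming sentence closes the question.

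A third reply is that the loss depends on what the 30% refers to. Under a count rule, dropping a missing subject and counting that subject as a non-responder lead to the same final decision. If 30% were the rate among all treated subjects, missing ones included, 25 treated subjects would still give 80.2%. Section 8.3 does not say which is meant, but a target of 25 evaluable subjects with replacement of the others implies the rate among evaluable subjects.

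Finally, the spare places never guaranteed 0.8. With 30 places and a 20% loss, the chance of reaching 25 evaluable is 43% and averaged power is 74.5%. That is true, but 57.6% is much lower.

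**Conclusion.** The concern holds. Sections 8.3 and 8.4 use the same 5 places twice, and under the ceiling of 30 no dropout allowance remains. The n = 25 design and its power of 0.8 hold only if every post-amendment subject is evaluable. With 6 or more responders still required, power is 76.8% at 24 evaluable and falls to 58.4% at 20. The double use costs about 2 to 5 points of averaged power at assumed non-evaluable rates of 2-5%, and 14 to 17 points if the whole 15-20% is non-evaluable.

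This rests on three readings: the ceiling of 30 includes the 5 excluded subjects, as the wording and the arithmetic of section 8.4 indicate; 30% is the rate among evaluable subjects; and the cut-off stays at 6. Under that cut-off, alpha falls from 3.3% to 1.1% as the number evaluable falls from 25 to 20, so the risk is a false negative. The point should be fixed, but it does not invalidate the test.

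**What to change.** 1. Reword the section 8.4 sentence to say that, after the 5 excluded subjects, the ceiling of 30 leaves 25 places and no allowance for dropout. Bring the dropout and replacement sentences of section 8.3 into line with it.
2. Replace the single power of 0.8 with power by number evaluable: 80.2, 76.8, 72.9, 68.6, 63.7 and 58.4% at 25 down to 20.
3. State that 6 or more responders are required if fewer than 25 are evaluable.

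The cost is one corrected sentence with matching edits in section 8.3, one new sentence and a short table. No extra patients are needed. These changes disclose the loss of power; they do not restore it.

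An optional addition is to analyse every post-Amendment L subject who takes a dose, with missing outcomes counted as non-response. This would replace the plan's own replacement rule and must be fixed without reference to accumulated response data. If that is not possible, it should be reported only as a sensitivity analysis beside the rule as written. The n = 25 rule then applies if all 25 are dosed; a subject enrolled but never dosed would still use a place. Power is 80.2% if 30% is the rate among all such subjects. If 30% is the rate among completers, it is 63.8% at 15% dropout (0.30 × 0.85 = 0.255) and 57.1% at 20% (0.30 × 0.80 = 0.24). The option settles the denominator but does not recover power in the second case.
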